3.2 DISCUSSION OF STUDY DESIGN, INCLUDING CHOICE OF CONTROL GROUPS

Children who have an abdominal solid organ injury visualized on abdominal computerized tomography form the study group. Computerized tomography is the current gold standard for the diagnosis of these injuries in children. The purpose for choosing children who have already undergone abdominal computerized tomography is to be able to compare the new imaging technique: contrast enhanced ultrasound, to the gold standard. Children from age 8 through 17 years have been chosen to assure that they are able to assent to the study. At least 1 of the 5 abdominal solid organs (liver, spleen, pancreas, left kidney, right kidney) will be injured per patient and each subject will serve as their own control. CTs will be interpreted by radiologists at the participating institution. Sonographers will be blinded to the results of the computerized tomography.

This study will take place at 7-10 participating institutions. Based on prior data, approximately 30 potentially eligible patients are expected to present at each institution per year. We estimate enrollment will take 2-3 years to enroll 132 subjects who complete the study.

3.3 SELECTION OF STUDY POPULATION

Subjects who fulfill the following eligibility criteria will be recruited regardless of their race or gender. Prior to receiving a CT scan, all menarchal females will have a urine pregnancy test as per clinical care. The results of this test can be found in the medical record. If the pregnancy test is positive, the subject will not receive a CT scan and will therefore not be eligible for the study. No pregnancy tests will be administered for research purposes.

3.3.1 Inclusion Criteria

To be eligible to participate in this trial, subjects must meet all of the following criteria:

All study participants must be:

- Hemodynamically stable, as determined by the trauma team
- Age 8 through 17 years
- Interpretable CT of the abdomen and pelvis that demonstrates at least one abdominal solid organ injury among the liver, spleen, pancreas, and kidneys
- Plan for observation or admission to the hospital
- Candidate for abdominal ultrasound based on body habitus
- Have a Glasgow Coma Score of 15
- Able to complete the study procedures within 48 hours of injury

3.3.2 Exclusion Criteria

Subjects meeting any of the following criteria will be excluded from the study:

- Known cardiac abnormality
- Pulmonary hypertension
- Known sensitivity to sulfur hexafluoride, polyethylene glycol 4000, distearoylphosphatidylcholine (DSPC), dipalmitoylphosphatidylglycerol sodium (DPPG-Na), or palmitic acid
- Unable to roll over
- Unable to assent
- Pregnant
- Lactating
- CT images not available for transmission to central image repository

3.3.3 Removal of Subjects from Therapy or Assessment

Stopping Point

The study will be suspended immediately for any two Serious Adverse Events and will not resume until an investigation by the DSMB has concluded that the study should resume.

3.3.3.1 Subject Withdrawal or Early Termination

Subjects could choose to discontinue from the study at any time, for any reason, specified or unspecified, and without prejudice. Subjects could be discontinued from the study for any of the following reasons:

- At the subject's or their parent/guardian's request
- At the discretion of the site Investigator, if deemed appropriate, for any reason, such as the subject's medical status worsening.

3.3.3.2 Planned Follow-up for Discontinued Subjects

The study has a single phase which lasts 50-90 minutes. We do not anticipate any discontinued subjects.

3.4 STUDY DRUG

3.4.1 Identity of Investigational Product

Lumason (sulfur hexafluoride lipid-type A microspheres) is the investigational product.

3.4.2 Packaging and Labeling

Lumason (sulfur hexafluoride lipid-type A microspheres) is available in a carton of five 5 mL single use vials. (NDC 0270-7099-16)

DOSAGE AND ADMINISTRATION

The recommended dose of Lumason for children is 0.03 mL/kg up to a maximum dose of 2.4mL injected into a peripheral intravenous catheter. This will be repeated once to ensure all organs are visualized. See individualization of dose below.

1. Follow the Lumason injection with a flush of 5 ml of 0.9% Sodium Chloride Injection, USP.
2. The maximum total dose for children as listed in the package insert should not exceed 2.4 mL in any 10-minute period. For this study, over any 10-minute period we intend to administer the approved dose of 0.03 mL/kg up to a maximum of 2.4 mL.
3. The maximum total dose for children as listed in the package insert should not exceed 4.8 mL in any one patient during the full time on study. In this study, we intend to administer a

total dose in any one patient during the full time on study of 0.06 mL/kg with a maximal dose of 4.8 mL.

3.4.3 Dosage Administered

Licensed study personnel will administer Lumason 0.03 mL/kg in two separate injections to a maximum of 2.4 mL per injection:

Injection 1: Image right side: right kidney and then liver (transverse and sagittal sweeps) and pancreas (transverse sweeps).

The second injection will be administered a minimum of 10 minutes after the first injection.

Injection 2: Image left side: left kidney and then spleen (transverse and sagittal sweeps) and pancreas (transverse sweeps).

The maximum dose will not exceed 0.03 mL/kg up to a maximum of 2.4 mL in any 10 minute period. The total allowable dose for any one patient is 0.06mL/kg up to a maximum of 4.8mL.

Following each Lumason contrast push injection, a flush of 5 mL of 0.9% sodium chloride will be administered intravenously.

3.4.4 Selection of Doses in the Study

The doses to be used have been chosen because they have been approved by the FDA for the visualization of focal liver lesions in children. The liver is one of the most common organs injured in trauma and it is expected that an ultrasound contrast dose that results in good visualization of the liver will also result in good visualization of the other abdominal organs. In addition, the selected dose, which may be repeated twice, is in line with the dose used in European studies which safely performed CEUS for abdominal solid injuries in children using SonoVue, the European brand-name for Lumason.

3.4.5 Investigational Product Accountability

The Sponsor will be responsible for Drug Accountability requirements for this trial. Lumason is an FDA approved agent available for sale for patient use in the United States. It will be purchased directly from the market, subject to the same manufacturing safety standards as other FDA approved agents on the market.

The agent will be stored in the research pharmacy equivalent at each institution and will be provided to study personnel once confirmation of consent has been obtained, per each participating hospital's research pharmaceuticals protocol. A drug accountability log will be

October 16, 2019

maintained by each sites' appropriately designated research pharmacy, including the study subject number alongside the product number of the vial used for that subject.

One sealed vial of agent will be used for each subject. The contents will be drawn up in sterile fashion by licensed study personnel and will be administered into an existing peripheral intravenous line. The dose used will vary by subject body weight as previously stated. At the completion of each subject's CEUS, all vials, including any residual agent left over, will be returned to the Research Pharmacy equivalent where it will be handled according to proper drug accountability procedures.

3.4.6 Prior and Concomitant Treatments

3.4.6.1 Prior and Concomitant Therapies

There are no prior or concomitant therapies in this study.

3.4.6.2 Prior and Concomitant Medications

There are no prior or concomitant medications in this study.

3.5 ASSESSMENTS

3.5.1 Schedule of Study Activities

Study Timeline

- Potential subjects who meet inclusion criteria, including having undergone a CT that demonstrates an abdominal solid organ injury, will be identified in the participating institutions' Emergency Departments. CTs may have been performed by a participating institution or a referring institution, in which case the CT has been delivered to the participating institution. These CTs will be read by the study staff at the participating institution and eligibility criteria will be assessed by reviewing medical records.
- Eligible subjects and their guardians will be approached and invited to participate. After sufficient time to allow thoughtful consideration of participation, appropriately designated study personnel will obtain consent from the guardian and assent from the

subject. Subjects may be consented and enrolled at any time during their hospital stay as long as the study procedures can be performed within 48 hours of injury.

- After evaluation and diagnostic studies are completed for the medical care of the subject, he/she will be taken to the Radiology department. If the subject is in the ICU, bedside ultrasounds may be performed instead of going to the Radiology department.
- Ultrasound personnel, blinded to the results of the CT and the medical records of the subject, will perform a greyscale/Doppler abdominal ultrasound and record the results.
- Licensed study personnel will then administer Lumason via an existing peripheral IV, and the sonographer will perform a contrast-enhanced abdominal ultrasound and record the results. Any physical findings on the subject's abdomen will also be recorded.
- The subject will be monitored for 30 minutes after the final Lumason injection as detailed in the Assessments sections.
- After completion of the ultrasounds, subsequent patient care will be as medically indicated.

3.5.2 Assessment of Efficacy

The presence or absence of an injury as well as the grade of the injury will be determined for the liver, spleen, pancreas, and each kidney in each patient. In addition, the presence or absence of peritoneal fluid as well as a rough estimate of the amount of fluid will be determined for each patient. These data will be determined by a sonographer for each of the study subjects. Inter-rater reliability will be determined by comparing the “real-time” read to a central read. These data will then be compared to the findings on computerized tomography, using the tomography as the standard. Sensitivity and specificity of the sonograms and the CEUS to identify injuries diagnosed on computerized tomography will be determined. Lumason will be considered effective if $\geq 90\%$ of the injuries identified by CT are visualized by CEUS.

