Number Planned	132 subjects are to complete this study: all in the treatment arm. Each patient will have at least one injured organ and their other organs will serve as controls compared to the other study subjects. Any subjects who do not complete the study will not count toward this number.
Major Inclusion Criteria	
 Age 8 to 17 years inclusive Abdominal solid organ injury visualized on computerized tomography Hemodynamically stable

October 16, 2019

Confidential

Name of Sponsor	[name], MPH
Coordinating Center	Boston Children's Hospital
Investigational Product	Lumason
ASSESSMENTS	
Efficacy	Lumason will be considered efficacious if $\geq 90\%$ of the abdominal solid organ injuries identified on computerized tomography are able to be visualized on contrast enhanced ultrasound.
Pharmacokinetics and Pharmacodynamics	No pharmacokinetics or pharmacodynamics will be performed.
Safety	Study subjects will be monitored for the development of any adverse reactions for 30 minutes following the final infusion of Lumason. No laboratory or other imaging studies are planned.
STATISTICAL METHODS AND ANALYSIS	
Efficacy	Lumason will be considered efficacious if $\geq 90\%$ of the abdominal solid organ injuries identified on computerized tomography are able to be visualized on contrast enhanced ultrasound.
Pharmacokinetics and Pharmacodynamics	No pharmacokinetics or pharmacodynamics will be performed.
Safety	Study personnel will monitor subjects for 30 minutes following the last infusion of Lumason. Patients will be maintained on a cardiopulmonary monitor through this time period. All adverse events will be graded according to the criteria specified by the Common Terminology Criteria for Adverse Events (CTCAE) Version 4.03 (NIH, June 14, 2010).

TABLE OF CONTENTS

	Page
ABBREVIATIONS AND DEFINITIONS	7
1. BACKGROUND	8
1.1 Name and Description of Investigational Product	9
1.2 Results of Nonclinical Studies	10
1.3 Results of Clinical Studies	10
2. STUDY OBJECTIVES.....	11
3. INVESTIGATIONAL PLAN.....	12
3.1 Overall Study Design and Plan	12
3.1.1 Study Endpoints	12
3.2 Discussion of Study Design, Including Choice of Control Groups	13
3.3 Selection of Study Population.....	13
3.3.1 Inclusion Criteria	14
3.3.2 Exclusion Criteria	14
3.3.3 Removal of Subjects from Therapy or Assessment.....	14
3.3.3.1 Subject Withdrawal or Early Termination	15
3.3.3.2 Planned Follow-up for Discontinued Subjects.....	15
3.4 Study drug.....	15

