Clinical experience with the use of CEUS has been limited in the United States. An as yet unpublished pilot study conducted by Zalieckas et al enrolled 18 children with 21 abdominal solid organ injuries identified on CT. Children underwent greyscale and Doppler ultrasound studies, then CEUS using the contrast agent Optison. They found that greyscale/Doppler ultrasound had a 45.2% sensitivity, 96.4% specificity, a 79.2% PPV, and an 85.3% NPV compared to CT. CEUS had an 85.7% sensitivity, 98.6% specificity, 94.7% PPV and 95.8% NPV. Two of the 3 missed injuries were in one 100 kilogram pediatric patient, suggesting that further trials be limited to patients otherwise considered to be good candidates for abdominal sonography.

Optison and Lumason are both contrast agents used to perform CEUS. Lumason is now FDA-approved for use in the characterization of focal liver lesions in adult and pediatric patients. It has been studied and used in Europe, under the brand name SonoVue, to identify abdominal solid organ injuries. Because Lumason is FDA-approved for a closely related indication in a pediatric population, we have chosen to use Lumason for this study.

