2. STUDY OBJECTIVES

The primary goal of the study is to evaluate whether the use of ultrasound contrast can improve the sensitivity and specificity of ultrasound in diagnosing abdominal solid organ injuries in pediatric patients, thereby making it a valuable diagnostic tool.

Since all patients entered on the study will have CT positive results, the primary endpoint is the proportion of patients for whom all organs identified by CT with injuries are also identified by CEUS, regardless of injury grade. This will provide an estimate of the sensitivity assuming CT as the gold standard.

The secondary objectives are to determine: 1) for each organ, the proportion of patients for whom the organ is identified by CT and CEUS as injured, 2) proportion of injuries identified by CEUS which are within 1 grade of the injury identified by CT, 3) the proportion of patients where the absence or presence of peritoneal fluid identified by CT is also identified by CEUS, and 4) the comparison between ‘real-time’ and centralized interpretation of CEUS images.

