3.1.1 Study Endpoints

- Primary endpoint is the proportion of patients for whom all organs identified by CT with injuries are also identified by CEUS, regardless of injury grade.
- Secondary endpoints:
 - For each organ, the proportion of patients for whom the organ is identified by CT and CEUS as injured.

- The proportion of injuries identified by CEUS which are within 1 grade of the injury identified by CT.
- The proportion of patients where the absence or presence of peritoneal fluid identified by CT is also identified by CEUS.
- The proportion of patients with agreement between ‘real-time’ and centralized interpretation of CEUS images.

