3.8 STATISTICAL METHODS PLANNED IN THE PROTOCOL AND DETERMINATION OF SAMPLE SIZE

3.8.1 Sample Size and Power Considerations

Sample size for the study was determined based on the precision of the confidence interval for the primary endpoint. This approach will be considered promising if the true proportion of subjects with all injuries identified by CT also identified by CEUS is greater than or equal to 90%. Assuming we observe 90% of subjects with all injuries identified by CT and by CEUS, a sample size of 132 patients will attain a two-sided 95% confidence interval with a width equal to 11%, with exact Clopper-Pearson lower and upper confidence limits of 83.6% and 94.5% respectively. For secondary endpoints, a sample size of 132 patients will produce 95% confidence intervals with a maximum width of 17.6%.

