3.8.2 Statistical Analysis Plan

We will summarize patient demographic and clinical characteristics using descriptive statistics: means, standard deviations, medians, and ranges for continuous measures; frequencies and proportions for categorical measures. For the primary objective, we will calculate the proportion and 95% confidence interval. For the secondary objectives, we will calculate the proportion and 95% confidence interval. We will also report the sensitivity and specificity of the CEUS relative to CT in identifying individual organ abnormalities in separate models and combined models. In the combined analysis, sensitivity and specificity will be estimated using random effects model or generalized estimating equations to adjust for potential correlation between organs within an individual. Statistical analysis will be performed using standardized packages (SPSS version 19.0 from SPSS Inc./IBM, Chicago, IL or SAS version 9.4 from SAS Institute Inc., Cary, NC.)

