3.8.4 Interim Analysis

An interim analysis will be conducted after the first 73 patients. At this time, the conditional power will be calculated. If the probability of obtaining a point estimate $\geq 90\%$ for the primary endpoint is less than 10% at the interim analysis, we will consider stopping the study for futility.

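### Efficacy is declared on at least 90% of injuries seen, but the primary endpoint, sample size, benchmark and futility rule count patients; the plan does not say which 90% decides.

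*Combined protocol and SAP*

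**What the plan says.** **Counting injuries.** Section 3.5.2 (Assessment of Efficacy) makes Lumason effective if at least 90% "of the injuries identified by CT are visualized by CEUS". The synopsis gives the same rule for efficacy under both Assessments and Statistical Methods: at least 90% "of the abdominal solid organ injuries identified on computerized tomography are able to be visualized on contrast enhanced ultrasound".

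**Counting patients.**
- Section 2: "the primary endpoint is the proportion of patients for whom all organs identified by CT with injuries are also identified by CEUS". Section 3.1.1 lists the same endpoint.
- Section 3.8.1 sizes the trial on this proportion and calls the approach promising if "the true proportion of subjects with all injuries identified by CT also identified by CEUS is greater than or equal to 90" percent.
- Section 3.8.4 takes the probability of a point estimate of at least 90%. If that probability "for the primary endpoint is less than 10% at the interim analysis, we will consider stopping the study for futility".

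**Analysis.** Section 3.8.2 reports the primary proportion with a 95% confidence interval. It also plans a combined organ-level sensitivity by random effects or GEE "to adjust for potential correlation between organs within an individual". Neither result is tied to a 90% criterion. The overall share of injuries seen is not among the endpoints in 3.1.1.

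**The concern.** The sentences that say when the product is efficacious use one unit, and everything the trial is built on uses another. The proportions coincide when every child has one injury or nothing is missed. Otherwise a child with two injuries, one of them missed, counts as a full failure on the patient scale but as one hit and one miss on the injury scale.

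Read literally, 3.5.2 could yield a declaration of efficacy when the primary endpoint is below 90%, or the reverse. Futility is also judged on a different quantity from the stated efficacy rule. If this is left open until results are known, the report could rest on whichever 90% was met.

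**Working it through.** **1. The plan's own figure.** Clopper-Pearson limits with x = 0.90 × 132 = 118.8 and n = 132 are 83.6% to 94.5%, width 11.0%, as 3.8.1 states. The nearest whole count meeting 90% is 119/132 = 90.2%, with exact limits 83.7% to 94.7%.

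**2. Injuries per child in the protocol's pediatric series.**
- The pilot in section 1 "enrolled 18 children with 21 abdominal solid organ injuries identified on CT": 21/18 = 1.17.
- The prospective series in 1.3 had 14 injuries in 12 children: 1.17.
- The retrospective series in 1.3, as reported, had 67 injuries in 67 children: 1.00.
- Pooled: (21 + 14 + 67)/(18 + 12 + 67) = 102/97 = 1.05.

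The value for this trial is an assumption.

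**3. The two rules at 132 patients.** The patient rule allows 132 − 119 = 13 failing patients. At 1.17 there are 132 × 21/18 = 154 injuries. The injury rule then needs 139 (0.90 × 154 = 138.6), so it allows 15 misses. At 1.05 (139 injuries) it needs 126 (0.90 × 139 = 125.1) and allows 13.

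**4. Worked cases.**
- 154 injuries, 15 misses in 15 different patients: 139/154 = 90.3% of injuries, but 117/132 = 88.6% of patients. The injury rule is met and the primary endpoint is below 90%.
- 139 injuries, 14 misses in 13 patients: 125/139 = 89.9% of injuries, but 119/132 = 90.2% of patients. This is the opposite split.

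**5. How often the rules split.** The calculation is an exact enumeration over 132 patients, of whom n2 have two injuries and the rest one. With q = 1 − sensitivity and within-patient correlation ρ, P(both missed) = q² + ρq(1 − q).

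| True injury sensitivity | 1.17 per child (n2 = 22), ρ = 0 / 0.5 | 1.05 per child (n2 = 7), ρ = 0 / 0.5 |
|---|---|---|
| 90% | 19.3% / 11.2% | 0.8% / 4.1% |
| 92.9% (13/14) | 11.5% / 5.5% | 0.3% / 2.4% |
| 95% | 1.6% / 0.7% | 0.04% / 0.4% |
| 96.4% (81/84) | 0.1% / 0.05% | 0.0% / 0.03% |

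At 1.00 per child the chance is zero. At 1.17 nearly all splits are the injury rule met and the patient rule failed (at 90%: 19.26% against 0.01% for ρ = 0; 10.10% against 1.13% for ρ = 0.5). At 1.05 every split goes the other way.

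**6. Chance of meeting each rule at 90% sensitivity and 1.17 per child.** Patient rule 0.33 (ρ = 0) to 0.44 (ρ = 0.5); injury rule 0.53.

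**The case against.** **The primary endpoint decides implicitly.** Sections 2 and 3.1.1 name one primary endpoint; 3.8.1, 3.8.2 and 3.8.4 size, report and monitor it; section 2 calls it an estimate of sensitivity. The injury sentences may be loose shorthand. This is the likeliest intention, and it is why the remedy is light. It is not conclusive: 3.8.1 says promising, and efficacious or effective is attached only to the injury rule.

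**The size rests on assumptions.** This stands. Injuries per child and correlation are not fixed by the plan, and the model allows at most two injuries although five organs are assessed. Results near the threshold are sensitive to whole-number rounding. None of the pediatric series would have split: the pilot gives 18/21 = 85.7% of injuries and, if the third miss was in a second child, 16/18 = 88.9% of patients; the prospective series gives 13/14 = 92.9% and 11/12 = 91.7%; the third is 100% on both.

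**Stronger readings that do not hold.**
- A reader might infer that 132 patients are too few for the injury proportion. In this model the effective number of injuries at 1.17 and ρ = 0.5 is 154²/(154 + 2 × 22 × 0.5) = 134.8, so precision is about what 3.8.1 states.
- A reader might infer that 3.8.1 (true proportion) and 3.8.4 (point estimate) contradict each other. One is a design benchmark and the other an interim trigger; they serve different purposes.
- A reader might infer that the lower confidence limit must reach 90%. No section suggests so.

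**The remedy picks a winner.** It does settle a success criterion, but in favor of the endpoint already named primary.

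**Conclusion.** The inconsistency is in the text and should be fixed. The efficacy sentences count injuries, the design counts patients, and nothing reconciles them.

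The consequence is material when true sensitivity is near 90% and several children have more than one injury. At the pilot's ratio, opposite verdicts have a chance of 11% to 19% at 90% sensitivity and 5.5% to 11.5% at 92.9%, a value the protocol itself cites. The risk is small at 95% and negligible at 96.4%. At the pooled 1.05 injuries per child it is 0.8% to 4.1% even at 90%. These figures assume 132 analysed patients, at most two injuries each and a correlation of 0 or 0.5.

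The documents do not support a claim that the sample size is wrong or that the verdicts will usually differ.

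**What to change.** 1. In the synopsis (both places) and 3.5.2, replace the injury-based sentence with: *Lumason will be considered efficacious if the observed proportion of analysed patients with every CT-injured organ identified by CEUS is at least 90% (at least 119 if 132 are analysed), reported with its exact 95% confidence interval.*
2. Keep injury- or organ-level sensitivity as a supporting result from the GEE or random-effects analysis already in 3.8.2.
3. In 3.8.1, add that meeting an observed 90% does not by itself show that the true proportion is at least 90%. For 119/132 the interval is 83.7% to 94.7%, and 119 or more successes still occur with probability 0.27 if the true proportion is 0.88. Do not add a lower-limit rule.

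**Cost.** Wording in four places, with no new patients or data, preferably before the results are examined. The price is a harder criterion if multiple injuries are fairly common (step 6 above).
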